4.1.1. Part A Single Ascending Dose Phase in Healthy Adult Subjects

Healthy adult subjects will be enrolled in 1 of 4 planned ascending dose cohorts. At the start of each cohort, 2 sentinel subjects will be randomized 1:1 to VIR-2218 or placebo. These subjects will be dosed concurrently and monitored for 24 hours; if the investigator has no safety concerns, the remainder of the subjects in the same cohort will be dosed. Vital signs, symptom-directed physical examination(s), and AEs will be reviewed by the investigator prior to dosing any additional subjects. The remaining subjects will be randomized 5:1 to receive a single dose of VIR-2218 or placebo.

Subject screening will occur no more than 4 weeks prior to the Day 1 visit. Eligible subjects will be confined to the clinical investigative site on Day -1 to determine continued eligibility and for predose assessments. Subjects in each cohort will be randomized to receive VIR-2218 or placebo within 48 hours prior to study drug administration. Subjects will receive a single dose of study drug on Day 1 (VIR-2218 or placebo). Subjects will be discharged from the clinical investigative site after all assessments are completed on Day 2.

Subjects will return to the clinical investigative site on an outpatient basis for safety, tolerability, and PK monitoring at specified timepoints through the last Post-dose Follow-up Visit (Week 12).

Based on review of the accumulated, available data in Part A, the SRC may recommend dosing of 2 optional cohorts. In addition to the optional cohorts, up to 8 “floater” subjects for Part A may be added to any cohort, as determined and approved by the SRC (see Section 4.5.2 and Appendix 6 for further information).

Fasting is not required for any study procedure/assessment.

4.1.2. Part B/C Multiple Ascending Dose Phase in Non-Cirrhotic Adult Subjects with Chronic HBV Infection on Nucleoside/Nucleotide Therapy

Non-cirrhotic adult subjects with chronic HBV infection on NUC therapy for ≥ 6 months will be enrolled in the Part B/C cohorts. Part B will enroll HBeAg-negative subjects. Part C will enroll HBeAg-positive subjects. Eligible subjects should have HBV DNA < 90 IU/mL. Each cohort in Part B/C will be composed of 4 subjects randomized 3:1 to VIR-2218 or placebo, respectively. There are 3 planned and 2 optional cohorts in Part B. There are 1 planned and 2 optional cohorts in Part C.

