Subjects enrolled in Part B/C of the study will remain outpatient. Subject screening will occur no more than 4 weeks prior to the Day 1 visit. Eligible subjects will undergo further assessments on Day 1 to qualify for study drug administration on Day 1. To exclude the presence of cirrhosis, screening will include a mandatory noninvasive assessment of liver fibrosis such as a FibroScan evaluation, unless the subject has results from a FibroScan evaluation performed within 6 months prior to screening or a liver biopsy performed within 1 year prior to screening that confirms the absence of Metavir F3 fibrosis or F4 cirrhosis.

Subjects in each cohort will be randomized 3:1 to receive VIR-2218 or placebo within 48 hours prior to study drug administration on Day 1. Subjects will return to the clinical investigative site at Week 4 to receive a second dose of the same study drug administered on Day 1. The decision to administer a second dose will be made based on Week 3 laboratory values in accordance with dose suspension/stopping criteria in Section 4.6.

CCI

Subjects will return to the clinical investigative site on an outpatient basis for safety, tolerability, PK, and antiviral activity monitoring at specified timepoints through the last Post-dose Follow-up Visit (Week 16). Additional HBsAg monitoring is required for subjects with HBsAg levels with a $> 10\%$ decrease from the Day 1 predose level at the Week 16 visit. Visits will occur

every 4 weeks starting at Week 20 up to Week 48 or until the HBsAg level returns to $\geq 90\%$ of the Day 1 predose level. Additional HBsAg monitoring may be discontinued at the Sponsor's discretion based on emerging data.

Based on review of the accumulated, available data in Parts A, B, and C, the SRC may recommend dosing of optional cohorts following the same stratification. In addition to the optional cohorts, a combined total of up to 16 "floater" subjects for Part B/C may be added to any cohort, as determined and approved by the SRC (see Section 4.5.5 and Appendix 6 for further information).

Fasting is not required for any study procedure/assessment. The assessments performed at each visit are described in Appendix 3 .

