4.6.2. Individual Subject Stopping Rules in Part B/C

Individual subjects in Part B/C who have received 1 dose of study drug will not receive a second dose if any the following criteria are met:

- Serum ALT > 10 × ULN
- Serum ALT > 5 × ULN, with no change (< 50% of baseline) in HBsAg
- Serum ALT or AST > 3 × ULN with a concomitant total bilirubin > 2 × ULN
- Any clinical manifestations of hepatic decompensation

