9.2 SUMMARY STATISTICS FOR PK DATA

9.2.1 *Summary statistics for plasma and urine concentration data*

The units of concentration with amount or concentration in the unit, will be presented as they are received from the analytical laboratories.

The actual sampling date and time and elapsed time relative to dosing time for plasma and urine data will be listed by subject and nominal sampling time, with time deviation (difference in minutes between nominal and actual sampling times) calculated, for all subjects with available concentration data, including subjects excluded from the PK analysis set.

Summary statistics of PK concentration data of VIR-2218 and its metabolites (n, arithmetic mean, standard deviation [SD], coefficient of variation [CV%], geometric mean, geometric CV%, median, minimum and maximum) will be calculated for each time point and summarised by treatment group for healthy subjects (part A) and CHB subjects (part B andC), respectively. Geometric CV% calculated as the square root of the exponentiated SD of the natural log transformed data ($\text{SQRT}(\exp(\text{sln}^2)-1)$), where appropriate.

When reporting individual values and descriptive statistics for VIR-2218 and metabolite plasma and urine and concentration data, the following rules will apply regarding rounding and precision:

- Descriptive statistics for PK concentration data will be reported to the same level of precision as the individual data for the minimum and maximum, and to 1 additional decimal place or 1 additional significant figure – depending on the reporting format of the original data with a maximum of 3 significant figures - for the mean (arithmetic and geometric), median and standard deviation.
- Between-subject CV% and geometric CV% will be reported as a percentage to 1 decimal place.
- Subjects with dosing deviations will be listed but excluded from the summary tables.

9.2.2 *Summary statistics for plasma and urine PK parameters*

Calculated PK parameters will be listed and summarized descriptively, including n, arithmetic mean, SD, minimum, median, maximum, coefficient of variation [CV(%)], geometric mean

(GM), geometric SD, geometric CV%; For t_{max} , only n, minimum, median, and maximum will be reported.

When reporting individual values and descriptive statistics for PK plasma and urine for VIR-2218 and its metabolites, the following rules will apply to rounding and precision:

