- Individual values for PK parameters will be reported to 3 significant figures.
- Descriptive statistics for PK parameters will be reported to 3 significant figures.
- Between-subject CV% and geometric CV% will be reported as a percentage to 1 decimal place.
- Data listings containing all documented data and all derived data will be generated.
- Missing data will not be imputed.
- Subjects with dosing deviations will be reported in the listings but excluded from the summary tables.

9.1 9.3 CONCENTRATION-TIME PROFILES

Individual (for each subject) and mean plasma VIR-2218 and metabolite concentrations will be displayed graphically in linear and semi-logarithmic plots of concentration versus time (hour) by treatment group separately for healthy subjects (part A) and CHB subjects (part B and C). The actual collection time will be used for plots of individual plasma concentrations and nominal time will be used for plots of mean plasma concentrations. Below the plots, the number of quantifiable concentrations per timepoint will be displayed.

Individual (for each subject) and mean urine VIR-2218 and metabolite concentrations will be displayed graphically in linear and semi-logarithmic plots of concentration versus time (hour), by treatment group separately for healthy subjects in part A and CHB subjects (part B and C). The actual collection time will be used for plots of individual plasma concentrations and nominal time will be used for plots of mean plasma concentrations. Below the plots, the number of quantifiable concentrations per timepoint will be displayed.

Subjects with dosing deviations will be excluded from the mean plots. They will be displayed in the individual plots with footnote.

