9.2 Plasma PK Parameters

Pharmacokinetic analysis will be performed on the plasma PK concentration data to determine PK parameters by non-compartmental analysis using Phoenix WinNonlin® software (version 8.1 or higher).

Actual sampling times will be used for the PK analysis and if the actual sampling time is not recorded, the nominal sampling time will be used.

PK parameters (applicable for single dose cohorts in part A, day 1-dose and day-29 dose of multiple dose cohorts in part B and C):

Due to the short plasma half-life of VIR-2218 and metabolite, pharmacokinetic analysis will be performed separately for day-1 dose and day-29 dose in patients in parts B/C.

The following PK parameters of VIR-2218 and its metabolites to be determined at defined timepoints include:

- **C_{max}** : Individual maximum concentration (C_{max}) values are directly determined from the plasma concentration time profiles for each subject.
- **t_{max}** : The time to attain C_{max} . If the same C_{max} concentration occurs at different time points, t_{max} is assigned to the first occurrence of C_{max} .
- **t_{last}** : Time of last measurable (positive) observed concentration

- **C_{last}**: Observed concentration corresponding to t_{last}.
- **AUC_{0-t}**: The areas under the curve spanning time interval from 0 to t (up to the last time point with measurable concentration). AUC_{0-t} will be calculated using the linear-up /logarithmic-down trapezoidal rule.

Linear trapezoidal rule:

The area of the trapezoid between the two data points (t₁, C₁) and (t₂, C₂) where C₂ ≥ C₁ will be computed by:

$$AUC_{t_1-t_2} = 0.5(t_2 - t_1)(C_1 + C_2)$$

Logarithmic trapezoidal rule:

The area of the trapezoid between the two data points (t₁, C₁) and (t₂, C₂) where C₂ < C₁ will be computed by:

$$AUC_{t_1-t_2} = \frac{((t_2 - t_1)(C_1 - C_2))}{\ln C_1 - \ln C_2}$$

- **AUC_{0-12hr}**: The area under the plasma concentration-time curve over the time interval from 0 to 12 hr using the linear-up /logarithmic-down trapezoidal rule.
- **AUC_{0-24hr}**: The area under the plasma concentration-time curve over the time interval from 0 to 24 hr using the linear-up /logarithmic-down trapezoidal rule.
- **AUC_{0-∞}**: The area under the plasma concentration-time curve over the time interval from 0 extrapolated to infinity will be calculated according to the following equation:

$$AUC_{0-\infty} = AUC_{0-t} + \frac{C'_t}{\lambda_z}$$

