9.6 DOSE PROPORTIONALITY FOR PK PARAMETERS

Dose proportionality will be evaluated separately for healthy subjects (part A) and day-1 dose of CHB subjects (part B and C) based on subjects without dosing deviations.

To assess dose proportionality, the natural log transformed, dose normalized $AUC_{0-\infty}$, AUC_{0-t} , AUC_{0-12} , AUC_{0-24} and C_{max} parameters will be evaluated using power model [2], with VIR-2218 dose level as the independent variable.

The power model for assessment of dose proportionality has the form of $\log(y) = \log(\beta_0) + \beta_1 \log(Dose)$ where y represents the PK parameter of interest. Dose proportionality is concluded if 90% CI for the β_1 falls within 0.7 to 1.43, which is less than 30% difference between doses for a given PK parameter.

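### The PK exclusion for dosing deviations is undefined and applies to the subject rather than the dose, so read as written a Week 4 deviation in Part B/C removes an unaffected Day 1 profile from the summaries

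*SAP*

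**What the plan says.** Four places in SAP section 9 carry the exclusion, each time for the subject:

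- 9.2.1, concentration summaries: "Subjects with dosing deviations will be listed but excluded from the summary tables".
- 9.2.2, PK parameter summaries: "Subjects with dosing deviations will be reported in the listings but excluded from the summary tables".
- 9.3, concentration-time profiles: "Subjects with dosing deviations will be excluded from the mean plots. They will be displayed in the individual plots with footnote".
- 9.6, dose proportionality, which in Part B/C uses the "day-1 dose of CHB subjects (part B and C) based on subjects without dosing deviations".

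None limits the exclusion to the dose that was affected. Neither document defines a dosing deviation; SAP section 6 describes only important protocol deviations in general terms. The PK Analysis Set (SAP 4.1.5) has no dosing-deviation condition, so an excluded subject stays in the set.

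The SAP section headed Plasma PK Parameters (its number is printed as 9.2 a second time) gives the short plasma half-life as the reason why "pharmacokinetic analysis will be performed separately for day-1 dose and day-29 dose in patients in parts B/C".

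On design, Protocol 4.1.2 states: "Each cohort in Part B/C will be composed of 4 subjects randomized 3:1 to VIR-2218 or placebo, respectively". It adds: "Subjects will return to the clinical investigative site at Week 4 to receive a second dose of the same study drug administered on Day 1". Protocol 4.6.2 lists laboratory and clinical criteria; if any is met, "Individual subjects in Part B/C who have received 1 dose of study drug will not receive a second dose".

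**The concern.** The unit of exclusion does not match the unit of analysis. The SAP treats the Day 1 and Day 29 doses as two separate PK assessments, but a fault in the second is enough to remove the subject from summaries of the first. Section 9.6 shows this most plainly: the Part B/C model uses only the Day 1 dose, yet the restriction to subjects without deviations is not tied to that dose.

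Characterising PK is a secondary objective of Part B/C, and the cohorts are very small. A rule that can drop a valid Day 1 profile costs up to a third of a dose group's Day 1 data for no gain in validity. Because the term is undefined, it is also open which events trigger the rule: a partial second dose, one given outside the ±2 day window in Protocol Appendix 3, or one not given at all. If that is still open when the data are unblinded by subject for the interim analysis (SAP 16.1), exclusions could be decided with results in view.

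**Working it through.** **1. Cohort size.** The planned total reproduces. Part A: 6 cohorts × 8 + 8 floaters = 56. Part B: 5 × 4 = 20. Part C: 3 × 4 = 12. With 16 floaters, Part B/C = 20 + 12 + 16 = 48, and 56 + 48 = 104, as in Protocol 9.8. Active subjects per unexpanded Part B/C cohort: 4 × 3/4 = 3.

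**2. Can a Week 4 fault reach the Day 1 profile?** Protocol Appendix 5 samples the Day 1 dose from predose to 24 hours and once more at Week 1. By the windows in Appendix 3, the Week 1 sample falls by Day 8 + 2 = Day 10, and the second dose not before Day 29 − 2 = Day 27. The gap is at least 17 days. A partial, late or missed second dose leaves the Day 1 profile unchanged.

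**3. Effect on a Day 1 summary.** Standard error = SD/√n.

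- 3 active falling to 2: √(3/2) = 1.22, so the standard error rises 22% at equal SD. Degrees of freedom for the SD go from 2 to 1.
- 6 active falling to 5: √(6/5) = 1.10, a rise of about 10%. Degrees of freedom go from 5 to 4.

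The second case arises because SAP 9.2.1 summarises by treatment group for the chronic hepatitis B subjects of Parts B and C, so a dose used in both parts may be pooled. In the SAP 3.6 list these doses are 50 mg and 200 mg; 20 mg and 100 mg occur only in Part B.

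**4. How likely is a loss?** The documents give no deviation rate. For an assumed per-subject rate p, the chance that at least 1 of 3 active subjects is affected is 1 − (1 − p)³:

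| p | 2% | 5% | 10% | 20% |
|---|---|---|---|---|
| At least 1 of 3 | 5.9% | 14.3% | 27.1% | 48.8% |

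**5. Effect on the dose-proportionality interval.** SAP 9.6 requires the 90% CI of the slope to lie within 0.7 to 1.43. Half-width = t(0.95, N − 2) × s/√Sxx, where s = √ln(1 + CV²) and Sxx is the sum of squares of log dose about its mean. Dose-normalising the parameter shifts the slope but not this half-width. The documents give no CV, so 20%, 30% and 50% are assumed.

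Worked case: CV 30%, protocol-planned cohorts, 12 active (3 at 50 mg, 3 at 100 mg, 6 at 200 mg).

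- s = √ln(1.09) = 0.294.
- All kept: Sxx = 8.25 × (ln 2)² = 3.964; 1.812 × 0.294/1.991 = 0.267.
- One 50 mg subject lost: Sxx = 6.545 × (ln 2)² = 3.145; 1.833 × 0.294/1.773 = 0.303.

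| Assumed CV | 12 active, all kept | One 50 mg subject lost | 18 active, all kept | One lost, worst case |
|---|---|---|---|---|
| 20% | 0.180 | 0.205 | 0.099 | 0.108 |
| 30% | 0.267 | 0.303 | 0.146 | 0.160 |
| 50% | 0.430 | 0.488 | 0.236 | 0.258 |

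The 18 active subjects are the six Part B/C dose groups of SAP 3.6 at an assumed 3 each; the worst case is the loss of a 20 mg subject. With 12 active and CV 30%, losing a 100 mg or 200 mg subject gives 0.271 or 0.281.

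**The case against.** The best defence is that the rule is unclear rather than wrong. With the term undefined, the restriction in 9.6 can be read, inside an analysis of the Day 1 dose, as meaning deviations in that dose. That reading is possible, but 9.2.1, 9.2.2 and 9.3 have no such anchor, and a programmer following the wording would drop the subject.

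Several stronger readings are tempting, and the documents do not support them.

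- **That the data are discarded.** They stay in the listings and the individual plots, and the subject stays in the PK Analysis Set.
- **That Day 1 PK is selected on tolerability.** The documented tolerability route to a missing second dose is Protocol 4.6.2. Withholding a dose under that rule follows the protocol, so it is not clearly a deviation. Selection arises only if such cases are counted, and the SAP does not say.
- **That precision collapses.** A 95% t-interval for a cohort mean would widen from 2.48 to 8.98 SD, about 3.6 times, when 3 falls to 2. The SAP plans no such interval; its PK summaries are descriptive. With pooling, 6 to 5 gives 1.05 to 1.24 SD.
- **That the dose-proportionality conclusion would flip.** With 12 active, CV 30% and an estimated slope of exactly 1, the lower limit moves from 0.733 to 0.697, just below 0.7. At CV 20% it stays above (1 − 0.205 = 0.795). At CV 50% it is already below with nobody lost (1 − 0.430 = 0.570). With 18 active and CV 30% it stays at 1 − 0.160 = 0.840 or higher.

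Replacement (Protocol 4.3) and floaters (Protocol 4.5.5) may restore numbers. Both are optional, and neither returns the excluded valid profile.

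**Conclusion.** The point holds as a minor but real defect of wording. Followed literally, the four rules let a second-dose deviation remove a Day 1 profile that it cannot have affected, against the SAP's own decision to analyse the two doses separately.

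The loss matters most in the descriptive Day 1 summary of a dose group with 3 active subjects, where one exclusion takes a third of the data and leaves 1 degree of freedom for the SD. It is milder where a dose is pooled over Parts B and C, and modest for the slope interval.

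The cohort figures assume unexpanded cohorts without replacement. The slope figures rest on assumed CVs and, for 18 subjects, on 3 active per listed group. How often this would happen cannot be derived from the documents. A reader might infer biased Day 1 PK or an unreliable dose-proportionality conclusion; neither is shown.

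**What to change.** Before the interim unblinding in SAP 16.1:

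1. Define a dosing deviation for PK purposes, including whether a dose outside the visit window, a partial dose and a dose not given count.
2. In SAP 9.2.1, 9.2.2, 9.3 and 9.6, make the exclusion dose-specific: drop Day 1 PK only for a Day 1 dosing deviation, and Day 29 PK only for a deviation that affects Day 29 exposure.
3. Confirm that a second dose not given, including one withheld under the protocol's stopping rules, leaves the Day 1 PK in the summaries and in the dose-proportionality model.

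This fits the SAP's existing practice of excluding single PK parameters when the extrapolated share of AUC exceeds 20%. The cost is SAP wording only, with no new data and no change to conduct. The Day 1 and Day 29 tables may then show different n.

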9.2 Plasma PK Parameters

Pharmacokinetic analysis will be performed on the plasma PK concentration data to determine PK parameters by non-compartmental analysis using Phoenix WinNonlin® software (version 8.1 or higher).

Actual sampling times will be used for the PK analysis and if the actual sampling time is not recorded, the nominal sampling time will be used.

PK parameters (applicable for single dose cohorts in part A, day 1-dose and day-29 dose of multiple dose cohorts in part B and C):

Due to the short plasma half-life of VIR-2218 and metabolite, pharmacokinetic analysis will be performed separately for day-1 dose and day-29 dose in patients in parts B/C.

The following PK parameters of VIR-2218 and its metabolites to be determined at defined timepoints include:

- **C_{max}** : Individual maximum concentration (C_{max}) values are directly determined from the plasma concentration time profiles for each subject.
- **t_{max}** : The time to attain C_{max} . If the same C_{max} concentration occurs at different time points, t_{max} is assigned to the first occurrence of C_{max} .
- **t_{last}** : Time of last measurable (positive) observed concentration

- **C_{last}**: Observed concentration corresponding to t_{last}.
- **AUC_{0-t}**: The areas under the curve spanning time interval from 0 to t (up to the last time point with measurable concentration). AUC_{0-t} will be calculated using the linear-up /logarithmic-down trapezoidal rule.

Linear trapezoidal rule:

The area of the trapezoid between the two data points (t₁, C₁) and (t₂, C₂) where C₂ ≥ C₁ will be computed by:

$$AUC_{t_1-t_2} = 0.5(t_2 - t_1)(C_1 + C_2)$$

Logarithmic trapezoidal rule:

The area of the trapezoid between the two data points (t₁, C₁) and (t₂, C₂) where C₂ < C₁ will be computed by:

$$AUC_{t_1-t_2} = \frac{((t_2 - t_1)(C_1 - C_2))}{\ln C_1 - \ln C_2}$$

- **AUC_{0-12hr}**: The area under the plasma concentration-time curve over the time interval from 0 to 12 hr using the linear-up /logarithmic-down trapezoidal rule.
- **AUC_{0-24hr}**: The area under the plasma concentration-time curve over the time interval from 0 to 24 hr using the linear-up /logarithmic-down trapezoidal rule.
- **AUC_{0-∞}**: The area under the plasma concentration-time curve over the time interval from 0 extrapolated to infinity will be calculated according to the following equation:

$$AUC_{0-\infty} = AUC_{0-t} + \frac{C'_t}{\lambda_z}$$

where C'_t is the predicted concentration at the time t (last time point with a measurable plasma concentration above the quantification limit) at which quantification was still possible, the calculation of λ_z is given below.

- **AUC_{%extrap}**: The percentage of the AUC that has been extrapolated beyond the last observed data point, calculated as:

$$AUC_{\%extrap} = \left(\frac{AUC_{0-\infty} - AUC_{0-t}}{AUC_{0-\infty}} \right) * 100$$

- **λ_z**: The apparent terminal rate constant λ_z will be estimated from a regression of ln(C) versus time over the terminal log-linear drug disposition portion of the concentration-time profiles. To calculate the elimination rate constant, the terminal data from a concentration-time curve will be used. Starting with the final non-BLQ data point and moving backwards, toward time zero, at least 3 data points not included C_{max} are fit to a linear regression. The number of data points used can be determined by maximizing the value adjusted-r² which defines the “best-fit” of the data.

The first order rate constant associated with the terminal (log-linear) portion of the curve will be estimated via linear regression of time vs. log concentration. The rules are that a minimum of three points is needed to define the terminal (log-linear) portion of the

curve, λ_z must be positive, and the selection is based on the best adjusted

square coefficient of regression (r^2). Additionally, if the adjusted r^2 does not improve, but is within 0.0001 of the largest adjusted R^2 value, the regression with the larger number of points is used.

The “adjusted” r^2 is calculated using the following equation:

$$\bullet \quad Adjusted\ r^2 = 1 - (1 - r^2) * \frac{(n-1)}{(n-2)},$$

where n = the number of data points used in the regression.

The slope of the line is equal to $-\lambda_z$ (i.e., the slope will be negative, but λ_z is a positive value).

If terminal concentration-time point(s) increases, this time point may be included if the $t_{1/2}$ estimate is reasonable. If λ_z is not determinable (for example, adjusted- r^2 value <0.8) then consequently only parameters not requiring λ_z will be reported. In addition, the lower (R_{start}) and upper (R_{end}) limit on time (h) for values to be included in the calculation of λ_z will be listed.

- **$t_{1/2}$:** The terminal half-life will be calculated from the terminal rate constant using the equation:

$$T_{1/2} = \frac{Ln(2)}{\lambda}$$

- **CL/F:** The total clearance will be calculated as following:

$$CL/F = \frac{D}{AUC_{0-\infty}}$$

where D is dose.

- **V_z/F:** The apparent volume of distribution based on terminal phase will be calculated according to the following equation:

$$V_z/F = \frac{CL/F}{\lambda_z}$$

Other important PK considerations

- The value of $AUC\%_{extrap}$ will be less than or equal to 20% for the $AUC_{0-\infty}$ to be considered well estimated. If this proportion is > 20%, then the values of $AUC_{0-\infty}$ will be treated with caution, and emphasis will be placed on AUC_{0-t} values (i.e. in subsequent statistical analyses).
- If $AUC\%_{extrap} > 20\%$, all elimination related parameters (λ_z , $AUC_{0-\infty}$, $t_{1/2}$, CL/F or CL/F_{ss} , and V_z/F or V_z/F_{ss}) will be presented in the listings but excluded from the calculation of summary statistics. All values excluded from the summaries should be flagged in the individual listings with an explanation for the exclusion.
- If data permits, the other PK parameters may be reported.
- If $t_{last} = t_{max}$, C_{max} will not be reported for that subject in the listings. It will be footnoted to indicate that sampling timepoints were not appropriate for that subject.
- If $t_{last} < 24hr$, AUC_{0-24hr} will only be reported when $AUC\%_{extrap} < 20\%$; It will be presented in the listing with footnote to indicate that AUC_{0-24hr} was extrapolated. In the summary

tables, the cohort will be footnoted to indicate that subjects with extrapolated AUC_{0-24hr} were included in the calculation of summary statistics.

- If $t_{last} < 12hr$, AUC_{0-12hr} will only be reported when $AUC\%_{extrap} < 20\%$; It will be presented in the listing with footnote to indicate that AUC_{0-12hr} was extrapolated. In the summary tables, the cohort will be footnoted to indicate that subjects with extrapolated AUC_{0-12hr} were included in the calculation of summary statistics.

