9.6. Pharmacokinetic/Pharmacodynamic Analysis

PK parameters of VIR2218 and possible metabolites will be computed using standard noncompartmental methods. Parameters may include, but not be limited to, plasma: maximum

concentration, time to reach maximum concentration, area under the concentration versus time curve (to the last measurable timepoint and to infinity), percent of area extrapolated, apparent terminal elimination half-life, clearance, and volume of distribution; urine: fraction eliminated in the urine and renal clearance, and will be listed and summarized using descriptive statistics. Other parameters may be calculated, if deemed necessary.

PK/pharmacodynamic analyses will be conducted to explore exposure-response relationships between PK parameters and selected antiviral variables. These analyses may include graphical plots, tabular summaries, and various linear and/or nonlinear analyses. Details of the analysis will be provided in the Statistical Analysis Plan.

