9.5 Urine PK Parameters

The following urine PK parameters of VIR-2218 and its metabolites will be determined for all single dose and multiple dose cohorts/parts:

- **Ae_{t1-t2}**: Total amount of drug excreted in urine from time t1 to t2 hours (cumulative and for each specific urine time intervals)
- **CLr**: Renal clearance of drug (cumulative) calculated as:

$$CLr = \frac{Ae_{t1-t2}}{Plasma\ AUC_{t1-t2}}$$

- **fe**- Fraction of the administered drug excreted into the urine (cumulative and for each specific urine time intervals)

$$fe = \left(\frac{Urinary\ excreted\ amount(mg)}{Dose(mg)} \right) * 100$$

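### SAP 9.2 applies CL/F and Vz/F to the metabolites using the VIR-2218 dose, which does not give metabolite clearance or volume; restrict both to VIR-2218 or relabel them (minor)

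*SAP*

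**What the plan says.** SAP 9.2 (Plasma PK Parameters) introduces one list for all analytes: "The following PK parameters of VIR-2218 and its metabolites to be determined at defined timepoints include". It runs without a break from Cmax to the volume of distribution. Three entries matter here:

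- AUC0-∞: "The area under the plasma concentration-time curve over the time interval from 0 extrapolated to infinity will be calculated according to the following equation", namely AUC0-t plus the extrapolated tail.
- CL/F: "The total clearance will be calculated as following", namely D/AUC0-∞, "where D is dose".
- Vz/F: "The apparent volume of distribution based on terminal phase will be calculated according to the following equation", namely (CL/F)/λz.

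No entry is limited to VIR-2218. There is no separate dose term, fraction-formed term, molar conversion or alternative label for a metabolite. On reporting, SAP 9.2.2 says "Calculated PK parameters will be listed and summarized descriptively". The rules that can remove CL/F or Vz/F from reporting or from the summaries are an extrapolated AUC above 20%, a λz that cannot be determined, and dosing deviations. None of them depends on the analyte.

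SAP 9.5 (Urine PK Parameters) also covers VIR-2218 and its metabolites. It defines fe as "Fraction of the administered drug excreted into the urine", computed as milligrams excreted over milligrams dosed, times 100. Protocol 9.6 is more general: "PK parameters of VIR2218 and possible metabolites will be computed using standard noncompartmental methods".

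**The concern.** A clearance formula of the form dose over AUC needs the amount of that analyte that entered the body. For VIR-2218 this is F·D. For a metabolite it is the amount formed, which nobody administers or measures. Putting the VIR-2218 dose in the numerator mixes how much metabolite is formed with how fast it is removed, and the SAP would call the result total clearance.

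What is at stake is interpretation. Clearance and volume are named among the secondary PK parameters for VIR-2218 and possible metabolites in SAP 2.3.2 and Protocol 3.1 and 3.2. A value labelled as metabolite clearance could be large because removal is fast or because formation is low, and the table would not show which. As an illustration, two groups with the same CLm but assumed fm of 0.1 and 0.2 would show values that differ by 0.2/0.1 = 2-fold.

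**Working it through.** The plan states no figure on this point, so there is none to reproduce. The check is algebraic, with assumed numbers for scale.

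**Inputs from the documents.** CL/F = D/AUC0-∞ and Vz/F = (CL/F)/λz, for parent and metabolites (SAP 9.2, Plasma PK Parameters). VIR-2218 is the only active product given; the comparator is saline (Protocol 6.2.1). D is therefore the VIR-2218 dose.

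**Inputs not in the documents.** fm (defined above), the molecular weights of parent (MWp) and metabolite (MWm), and the metabolite's own clearance CLm and volume Vm.

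**Step 1, clearance.** Under linear kinetics and in molar units, AUCm = F·fm·D/CLm. Hence

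D/AUCm = CLm/(F·fm).

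Relative to CLm/F, the multiple is 1/fm. Example with assumed D = 200 mg, F = 1, fm = 0.1, CLm = 10 L/h and equal molecular weights: AUCm = 0.1 × 200/10 = 2 mg·h/L, and D/AUCm = 200/2 = 100 L/h against a true 10 L/h.

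**Step 2, mass units.** In mass units AUCm gains a factor MWm/MWp, so D/AUCm = [CLm/(F·fm)] × (MWp/MWm). With an assumed MWm/MWp of 0.95 and fm = 0.1, the multiple is 10/0.95 = 10.5.

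**Step 3, volume.** Vz/F divides the Step 1 result by the observed terminal slope. If metabolite elimination is the slower process, that slope is the metabolite's own and only the 1/fm factor remains. If formation is slower, the slope belongs to the parent. Take an assumed one-compartment example with ka = 0.5/h, parent CL = 20 L/h and V = 60 L, metabolite CLm = 10 L/h and Vm = 20 L. The parent slope is 20/60 = 0.333/h and the metabolite's own rate is 10/20 = 0.5/h, so the extra factor is 0.5/0.333 = 1.5.

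| Assumed fm | CL/F multiple, 1/fm | Vz/F multiple if formation-limited, 1.5/fm |
|---|---|---|
| 0.05 | 20 | 30 |
| 0.1 | 10 | 15 |
| 0.25 | 4 | 6 |
| 0.5 | 2 | 3 |
| 0.9 | 1.11 | 1.67 |
| 1 | 1 | 1.5 |

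Numerical integration of the same model, with the slope fitted from 30 to 36 h (0.329/h), gave the same CL/F multiples. The Vz/F multiples were 30.4, 15.2, 6.1, 3.0, 1.7 and 1.5.

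**Step 4, can fm be recovered?** No. Metabolite AUC supplies one equation in the combination CLm/(F·fm), and the metabolite is never dosed on its own. Renal clearance (Ae over AUC, SAP 9.5) does not use the dose and is sound for either analyte.

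**Step 5, fe.** On a molar basis the metabolite fraction is (Ae/MWm)/(D/MWp) = (Ae/D) × (MWp/MWm). The SAP's milligram ratio therefore equals the molar fraction times MWm/MWp. At an assumed ratio of 0.95 it reads 5% low in relative terms.

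**The case against.** **The plan may not intend this.** The SAP never writes out the VIR-2218 dose divided by a metabolite AUC. That follows from joining a shared list heading to a generic D. The endpoint sections and Protocol 9.6 describe clearance and volume as parameters that may be reported, and the table list in SAP 18 is redacted, so the metabolite tables cannot be seen. This stands as a reason for caution about what will be tabulated. It does not settle the matter, because the optional wording is not in the SAP 9.2 list, which describes its parameters as ones to be determined. A programmer who followed that list would compute both for the metabolites.

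**The values are not arithmetically wrong.** A reader might infer that the reported numbers will simply be in error. D/AUCm is a reproducible apparent quantity; the fault lies in its label and the reading it invites. This objection stands.

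**The size is hypothetical.** A reader might also infer that these parameters would mostly reflect low metabolite formation, or would be inflated many-fold. The documents give no fm, and at fm near 1 the CL/F multiple is close to 1. Neither inference is supported.

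**Little depends on it.** SAP 3.3 plans no hypothesis tests. Dose proportionality (SAP 9.6) uses only AUCs and Cmax, and PK/PD work is outside the SAP (section 10). Healthy and HBV subjects are summarised separately, and no clearance comparison between them is planned. A false healthy-versus-HBV difference is therefore something a reader might draw from the tables, not a planned result. This stands and limits the severity.

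**The fe point may be trivial.** A mass ratio is a legitimate quantity, and the assay's reporting basis is not stated. It stands only as a request to fix the basis.

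**Conclusion.** The concern holds as a minor correction. As written, SAP 9.2 produces for each metabolite a quantity equal to CLm/(F·fm), with a molecular-weight ratio in mass units, under the name of total clearance. The volume carries the same factor, plus a slope distortion if the metabolite is formation-limited. Neither is the metabolite's own parameter, scaled only by F as the label implies, unless fm = 1 on a molar basis; for the volume, the slope must also not be formation-limited.

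The size cannot be determined from the documents. The 20-fold to 1-fold range for CL/F rests entirely on assumed fm from 0.05 to 1 and on linear kinetics. The 1.5 volume factor rests on one assumed example. The fe effect is likely small, and its size is equally undeterminable.

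VIR-2218 CL/F and Vz/F, metabolite Cmax, tmax and AUC, renal clearance, and the safety and antiviral results are unaffected. The parameters at issue are descriptive secondary PK results.

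**What to change.** 1. In SAP 9.2 (Plasma PK Parameters), limit CL/F and Vz/F to VIR-2218. Alternatively, keep metabolite versions but label them as apparent values, CLm/(F·fm) and Vz,m/(F·fm), and state the dose and molar basis. If the volume is kept, add a note that it is not Vz,m/(F·fm) when the terminal slope is formation-limited. Restriction to the parent is simpler.
2. In SAP 9.5, convert metabolite Ae to parent molar equivalents before dividing by dose for fe.
3. Optional: report molar metabolite-to-parent ratios for AUC and Cmax, which describe relative exposure without needing fm.

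The cost is a few lines of SAP text and a small programming change, with no new samples or data. Under the first option, two metabolite parameters without a clear meaning are dropped.
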